## 6.6. Dose Modification

### 6.6.1. Dose Modification and Toxicity Management of LY3475070 for Non-immune-mediated AEs Associated with LY3475070 and/or in Combination with Pembrolizumab

Patient may receive up to 2 dose reductions for AEs attributed to LY3475070. LY3475070 treatment may be interrupted, dose reduced or discontinued due to toxicity per the tables below.

Patients who have dose delays of more than 14 days, unless a different duration is specified in the above table, should permanently discontinue from the study.

Due to its MOA, LY3475070 may induce irAEs that could affect any organ of the body. Previous trials with agents inhibiting the adenosine pathway have not reported irAEs to the same incidence rate as seen with other check point inhibitors such as CTLA4 or PD-1/L1. From the ongoing A2AR antagonist single agent data only rash/pruritus, and elevated LFTs have been reported. In the event other irAEs occur please consult the table provided in Section 6.6.1.2 for management of irAEs.

Related AEs	Toxicity Grade or Conditions (CTCAE v5.0)	Action Taken to Therapy	AE Management	Monitor and Follow-up
Non hematologic				
Acneiform Rash	Grade 1	Continue treatment	Initiate topical prophylactic antibiotic (e.g., clindamycin). Consider using low potency topical steroids (e.g., hydrocortisone 2.5%)	Monitor for worsening signs and symptoms.
	Grade 2	Withhold therapy until $\leq$ Grade 1 (for recurrent Grade 2, or toxicity lasting more than 2 weeks proceed as Grade 3). If immune mediated rash is suspected see below table for management of immune mediated AE's).	Initiate oral antibiotic (e.g., doxycycline). Initiate low potency topical steroid, if not already started. Consider skin biopsy if immune mediated toxicity is suspected	Monitor for worsening signs and symptoms weekly

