	Grade 2	Continue treatment if immune mediated transaminitis is not suspected. Hold LY3475070 if immune mediated transaminitis is suspected (see below table for management of immune mediated AE's).	Review concomitant medications and alcohol use Consider hepatology consultation and rule out biliary obstruction due to disease progression Consider biopsy if immune mediated transaminitis suspected.	Monitor LFTs every 2-5 days until ≤Grade 1 (see protocol section 8.2.1.1)
	Grade 3	Hold LY3475070 until ≤Grade 1. Resume LY3475070 treatment at 1 DL lower if the patient has no evidence of drug induced hepatocellular injury. Patients with evidence of drug induced hepatocellular injury (i.e., transaminase ≥3XULN and total bilirubin ≥2XULN should	Review concomitant medications and alcohol use Consider hepatology consultation	Monitor LFTs every 2-5 days until ≤Grade 1 (see protocol section 8.2.1.1)

Related AEs	Toxicity Grade or Conditions (CTCAE v5.0)	Action Taken to Therapy	AE Management	Monitor and Follow-up
		permanently discontinue LY3475070 treatment.		
	Grade 4	Permanently discontinue LY3475070 treatment	Review concomitant medications and alcohol use Consider hepatology consultation.	Monitor LFTs every 2-5 days until ≤Grade 1 (see protocol section 8.2.1.1).
CCI				
Fatigue	Grade 1	Continue treatment	Manage per routine clinical practice and/or institutional guidelines	
	Grade 2	Continue treatment	Manage per routine clinical practice and/or institutional guidelines	
	Grade 3	Withhold LY3475070 until resolution ≤ grade 1, if resolved within 7 days then resume treatment.	Manage per routine clinical practice and/or institutional guidelines	

Related AEs	Toxicity Grade or Conditions (CTCAE v5.0)	Action Taken to Therapy	AE Management	Monitor and Follow-up
		If grade 3 persist over 7 days then dose reduce one level. If recurrence after continuing treatment dose reduce one level.		
Non-Hematologic Toxicity 	Grade 1	Continue LY3475070 treatment	Manage per routine clinical practice and/or institutional guidelines	
	Grade 2	Withhold LY3475070 treatment until resolution to ≤ grade 1 for recurrent Grade 2, or toxicity lasting more than 2 weeks proceed as Grade 3	Manage per routine clinical practice and/or institutional guidelines	
	Grade 3 or recurrent Grade 2	Withhold treatment until resolution to ≤ grade 1 and then reduce dose one level.	Manage per routine clinical practice and/or institutional guidelines	

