Nephritis: grading according to increased creatinine or acute kidney injury	Grade 2	Withhold	
 
Administer corticosteroids (prednisone 1 to 2 mg/kg or equivalent) followed by taper
 
	
 
Monitor changes of renal function
 

	Grade 3 or 4	Permanently discontinue		

irAEs	Toxicity grade (CTCAE V5.0)	Action with pembrolizumab and LY3475070	Corticosteroid and/or other therapies	Monitoring and follow-up
Myocarditis	Grade 1 or 2	Withhold	
 
Based on severity of AE administer corticosteroids
 
	
 
Ensure adequate evaluation to confirm etiology and/or exclude other causes
 

	Grade 3 or 4	Permanently discontinue		
All Other immune-related AEs	Persistent Grade 2	Withhold	
 
Based on severity of AE administer corticosteroids
 
	
 
Ensure adequate evaluation to confirm etiology or exclude other causes
 

	Grade 3	Withhold or discontinue based on the event e		
	Recurrent Grade 3 or Grade 4	Permanently discontinue		

a AST/ALT: >3.0 to 5.0 x ULN if baseline normal; >3.0 to 5.0 x baseline, if baseline abnormal; bilirubin: >1.5 to 3.0 x ULN if baseline normal; >1.5 to 3.0 x baseline if baseline abnormal

b AST/ALT: >5.0 to 20.0 x ULN, if baseline normal; >5.0 to 20.0 x baseline, if baseline abnormal; bilirubin: >3.0 to 10.0 x ULN if baseline normal; >3.0 to 10.0 x baseline if baseline abnormal

c AST/ALT: >20.0 x ULN, if baseline normal; >20.0 x baseline, if baseline abnormal; bilirubin: >10.0 x ULN if baseline normal; >10.0 x baseline if baseline abnormal

d The decision to withhold or permanently discontinue pembrolizumab is at the discretion of the investigator or treating physician. If control achieved or ≤ Grade 2, pembrolizumab may be resumed.

e Events that require discontinuation include but are not limited to: Guillain-Barre Syndrome, encephalitis, Stevens-Johnson Syndrome, and toxic epidermal necrolysis.

Abbreviations: AE = adverse event; ALT = alanine aminotransferase; AST = aspartate transaminase; GI = gastrointestinal; irAE = immune-related adverse event; IV = intravenous; ULN = upper limit of normal

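### The permanent stop for drug-induced liver injury is printed only in the Grade 3 row of Section 6.6.1, although its thresholds can be met at Grade 2, where that row lets dosing continue

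*Protocol*

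**What the plan says.** The table in Protocol Section 6.6.1 gives LY3475070 actions by grade for raised AST/ALT or bilirubin.

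- **Grade 2 cell.** "Continue treatment if immune mediated transaminitis is not suspected"; hold if it is suspected. The management column asks sites to consider hepatology advice and "rule out biliary obstruction due to disease progression". Liver tests are repeated every 2 to 5 days.
- **Grade 3 cell.** Hold until Grade 1 or better, then resume one dose level lower if there is no evidence of drug-induced hepatocellular injury. Next comes: "Patients with evidence of drug induced hepatocellular injury (i.e., transaminase ≥3XULN and total bilirubin ≥2XULN should" stop LY3475070 permanently (the verb follows after a page break in the same cell).

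Section 6.6.1 prints no numerical limits for the liver grades. Footnote a to the irAE table in Section 6.6.2 gives them for Grade 2: "AST/ALT: >3.0 to 5.0 x ULN if baseline normal; >3.0 to 5.0 x baseline, if baseline abnormal" and "bilirubin: >1.5 to 3.0 x ULN if baseline normal". Footnote b starts Grade 3 above 5.0×ULN for AST/ALT and above 3.0×ULN for bilirubin when baseline is normal. Both tables grade by CTCAE v5.0.

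**The concern.** The protocol names this laboratory pattern, when drug-induced, as a reason to stop a first-in-human drug for good. Yet the sentence sits in a row that a patient can miss while meeting its thresholds. Section 6.6.1 covers non-immune-mediated events, so direct drug injury at Grade 2 falls on the branch that says continue.

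The stop sentence supports two readings. It names no grade, so it can stand as a general rule. It also completes the Grade 3 resume rule printed just before it, so it can be taken as Grade 3 only. Two sites that make the same causal judgement on the same results could act in opposite ways, and a patient meeting the protocol's own injury definition could stay on drug. What is at stake is patient safety and consistent action across sites.

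**Working it through.** No power or error-rate figure is involved. The check compares thresholds and then looks for any other rule that fixes the action.

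**Inputs** (T = ALT or AST, B = total bilirubin, both as multiples of ULN, normal baseline)

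- Stop sentence, Section 6.6.1: T ≥ 3.0 and B ≥ 2.0.
- Grade 2, Section 6.6.2 footnote a: 3.0 < T ≤ 5.0; 1.5 < B ≤ 3.0.
- Grade 3 entry, footnote b: T > 5.0 or B > 3.0. Either is enough, because the row covers raised AST/ALT or raised bilirubin.

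**Step 1: overlap.** Combining the stop thresholds with the two Grade 2 ranges gives 3.0 < T ≤ 5.0 and 2.0 ≤ B ≤ 3.0. The stop thresholds therefore lie below Grade 3 by 5.0 − 3.0 = 2.0×ULN on transaminase and 3.0 − 2.0 = 1.0×ULN on bilirubin.

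**Step 2: example.** T = 4, B = 2.5. Both are Grade 2, and 4 ≥ 3.0 and 2.5 ≥ 2.0. If the injury is judged drug-induced and not immune-mediated, the Grade 2 cell says continue; the stop sentence, read as general, says stop permanently.

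**Step 3: lower edge.** At T = 3.0 exactly, the transaminase is not yet Grade 2, but B = 2.0 is, so the Grade 2 row still applies.

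**Step 4: other rules that reach this pattern.**

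| Rule | What it requires | Limit |
|---|---|---|
| DLT stop (6.1.1.1) | Stop for ALT/AST ≥ 3×ULN with bilirubin > 2×ULN, no cholestasis | Phase 1a, first 28 days only |
| Unacceptable toxicity (7.1) | Mandatory stop, any grade, both phases | Term not defined |
| Special hepatic data (8.2.1.1.1) | Extra data for the combined pattern, whatever the alkaline phosphatase | No dosing action |
| Event of clinical interest (8.3.7) | Report to sponsor | Only if alkaline phosphatase < 2×ULN; no dosing action |
| Repeat liver tests (6.6.1, 8.2.1.1) | Retest, look for causes | No dosing action |
| irAE liver row and note (6.6.2) | Withhold at Grade 2, consult sponsor | Only if an irAE is suspected |
| Delay rule (6.6.1): "Patients who have dose delays of more than 14 days" | Discontinue | Only if dosing was held |

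Outside the 28-day window, no rule specifically prescribes a stop for T and B in the Step 1 region. The last two rows do not reach the continue branch at all.

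**The case against.** The strongest case on the other side has four parts.

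- **The 3×/2× floor makes sense inside the Grade 3 row.** One raised analyte is enough for Grade 3, so ALT 6×ULN with bilirubin 2.2×ULN, or bilirubin 3.5×ULN with ALT 4×ULN, both need a lower limit on the second analyte. This stands. A reader might infer that the table contradicts itself; it does not. It is ambiguous, and one of the two readings leaves no gap.
- **Layout does not settle the reading.** The general non-hematologic Grade 2 row prints its own escalation, "for recurrent Grade 2, or toxicity lasting more than 2 weeks proceed as Grade 3", and the acneiform rash row does the same. A reader might conclude that anything not printed in a row does not apply to it. But the rash section also places a diagnosis-based permanent stop, for Stevens-Johnson syndrome or toxic epidermal necrolysis, in a Grade 3 cell. That is the closer parallel and weakens the inference.
- **Stopping at Grade 2 is never forbidden.** Section 6.6.1 introduces its table permissively, and unacceptable toxicity under Section 7.1 is a mandatory reason to stop. This also stands, but the term is undefined, so the decision goes back to site judgement.
- **The exposed case is narrow.** It must be drug-induced, not suspected to be immune-mediated, not obstructive, no higher than Grade 2, and outside the DLT window. This is true and limits the expected number, though Phase 1b alone may enrol up to about 140 patients with no DLT stop.

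**Conclusion.** The concern holds as an ambiguity in a safety rule. With normal baseline values, ALT/AST above 3.0 and up to 5.0×ULN together with bilirubin of 2.0 to 3.0×ULN meets the protocol's injury thresholds at Grade 2. Read row by row, the table then permits continued dosing after Day 28 in Phase 1a and at any time in Phase 1b. How many patients this would touch cannot be derived, as the documents give no event rate.

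The conclusion assumes that the grade limits in the Section 6.6.2 footnotes also apply in Section 6.6.1, which the shared CTCAE version supports. It also takes the stop to be a causal judgement and not a pure laboratory trigger.

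Two stronger inferences are not supported:

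- **A much wider zone for abnormal baselines.** Grades then scale with baseline (Grade 3 is ">5.0 to 20.0 x baseline, if baseline abnormal"), and Section 8.2.1.1.1 has a marker of at least 2×baseline with bilirubin at least 2×ULN. But that marker triggers data collection, not a dosing action, so it cannot define where dosing rules conflict. The size given here is for normal baseline only.
- **Damage to dose selection.** Events meeting DLT criteria after the window, or in Phase 1b, still count as DLT-equivalent (Section 6.1.1.2), and Section 9.4.4 includes DLT-equivalents in the safety summaries. No statistical figure is affected.

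**What to change.** Leave the Grade 3 sentence unchanged and add one exception to the Grade 2 liver cell, for example:

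*Exception: if there is evidence of drug-induced liver-cell injury (transaminase ≥3×ULN together with total bilirubin ≥2×ULN, not accounted for by biliary obstruction or cholestasis, disease progression, or confirmed Gilbert's syndrome), stop LY3475070 permanently.*

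The exclusions follow from the protocol. The Grade 2 row already asks for obstruction to be ruled out, the matching DLT requires absence of cholestasis, Phase 1a enrols pancreatic cancer, and patients with confirmed Gilbert's syndrome may enter with bilirubin up to just under 3×ULN (Section 5.1).

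Do not replace the 3×ULN limit with a multiple of baseline. Take baseline ALT 2.4×ULN (entry requires below 2.5×ULN), now 4.0×ULN, with bilirubin 3.5×ULN from a normal baseline and a judgement of drug injury. This is Grade 3, and the present text stops the drug. Under a 2×baseline rule, 4.0/2.4 = 1.67, so that stop would be lost.

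Cost: one sentence. ALT, AST, total and direct bilirubin and alkaline phosphatase are already in the chemistry panel (Appendix 2), taken weekly in Cycle 1 and every 3 weeks afterwards. The small downside is that a few Grade 2 patients who would have continued or been held would stop.

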#### Dose-Limiting Toxicities

Hematologic Toxicity
• Grade 3 thrombocytopenia associated with clinically significant bleeding and requiring platelet transfusion or Grade 4 thrombocytopenia of any duration
• Grade $\geq 3$ febrile neutropenia
• Grade $\geq 3$ anemia requiring a blood transfusion
• Other Grade $\geq 4$ toxicity, excluding toxicities listed below this table
Nonhematologic Toxicity – Nonlaboratory
• Grade $\geq 3$ irAE
• Grade $\geq 3$ colitis or noninfectious pneumonitis
• Grade $\geq 3$ pneumonitis or Grade 2 pneumonitis that does not show clinical improvement within 3 days after initiation of optimal medical management including corticosteroids therapy, which is then treated as Grade 3
• Grade $\geq 3$ nausea, vomiting or diarrhea that lasts more than 48 hrs despite optimal supportive care
• Grade $\geq 3$ fatigue lasting $>7$ days
• Grade $\geq 3$ hypertension despite maximal medical therapy
• Grade $\geq 3$ tachycardia
• Any other Grade $\geq 3$ toxicity
• Immune-related adverse event that necessitated permanent discontinuation of study drug(s), regardless of grade
Nonhematologic Toxicity – Laboratory/Investigations
• Any Grade $\geq 3$ laboratory abnormality except for specific exceptions listed below
• ALT or AST: 
 
○ <math>>8 \times</math> ULN
 
○ <math>\geq 2</math>-fold above the patient's baseline value that lasts <math>>7</math> days,
 
○ <math>\geq 3 \times</math> ULN with concomitant bilirubin <math>>2 \times</math> ULN, in the absence of cholestasis
 
○ Total bilirubin <math>>3 \times</math> ULN
 
○ <math>\geq</math>Grade 3 amylase or lipase that is associated with symptoms or clinical manifestations of pancreatitis
 

Please refer to Section 8.2.1.1 for additional hepatic safety monitoring guidance.

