	Grade 3	Withhold therapy until $\leq$ grade 1 then dose reduce LY3475070 (if rash worsens or does not improve in two weeks permanently discontinue) If Stevens–Johnson syndrome or toxic epidermal necrosis permanently discontinue patient	Initiate oral antibiotic (e.g., doxycycline). Initiate systemic corticosteroid (e.g., prednisone 0.5 mg/kg daily (maximum dose, 40 mg). Consider dermatology consultation.	Monitor for worsening signs and symptoms weekly until improvement to $\leq$ Grade 1. Resume LY treatment with 1 DL reduction. If rash does not improve or worsens after 2 weeks of treatment, discontinue LY permanently. If Stevens–Johnson syndrome or toxic epidermal necrolysis is suspected, discontinue permanently.
	Grade 4	Permanently discontinue	Initiate oral antibiotic (e.g., doxycycline). Initiate systemic corticosteroid (e.g., prednisone 0.5 mg/kg daily (maximum dose, 40 mg). Consider dermatology consultation.	
Diarrhea	Grade 1	Continue LY3475070 treatment. Start loperamide 4 mg initially, followed by 2 mg every 4 hours or after each stool.	Consider discontinue of lactose containing products	

Related AEs	Toxicity Grade or Conditions (CTCAE v5.0)	Action Taken to Therapy	AE Management	Monitor and Follow-up
	Grade 2	Continue LY3475070 treatment if Grade 2 diarrhea lasts <48 hours. Hold LY3475070 treatment if Grade 2 diarrhea lasts ≥48 hrs treatment until resolution to ≤ Grade 1.	Start loperamide 4 mg initially, followed by 2 mg every 4 hours or after each stool. Encourage oral hydration. If immune mediated colitis is suspected, consider GI consultation and biopsy.	
	Grade 3	Hold LY3475070 until resolution to Grade ≤ 1. Resume LY at 1 DL lower upon recovery.	If not already done, start loperamide 4 mg initially, followed by 2 mg every 4 hours or after each stool. Consider hospitalization for symptom and fluid management and GI consultation.	
	Grade 4	Permanently discontinue LY3475070 treatment	Consider hospitalization for symptom and fluid management, hydration and GI consultation.	
AST/ALT elevation or Increased bilirubin	Grade 1	Continue LY3475070 treatment	Review concomitant medications and alcohol use	

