	Grade 4	Permanently discontinue	Manage per routine clinical practice and/or institutional guidelines.	
Hematologic toxicity				
Neutropenia	Grade 1	Continue treatment		
	Grade 2	Continue treatment		
	Grade 3	Withhold LY3475070 until resolution ≤ grade 1 for recurrent Grade 3, or toxicity lasting more than 2 weeks proceed as grade 4.  If febrile neutropenia then dose reduce one level upon resolution ≤ grade 1	If patient is above 38.0° C on 2 separate occasions and or associated with signs or symptoms of sepsis start intravenous in accordance with the local hospital neutropenic sepsis guidelines G-CSF support may be given as deemed appropriate by the physician per institutional guidelines	Perform CBC weekly ≤Grade 3
	Grade 4	Withhold LY3475070 until resolution ≤ grade 1 then resume at one reduced DL. If neutropenia is longer than 5 days discontinue patient	If patient is above 38.0° C on two separate occasions and or associated with signs or symptoms of sepsis start intravenous in accordance with the local hospital neutropenic sepsis guidelines.	Perform CBC weekly ≤Grade 3

Related AEs	Toxicity Grade or Conditions (CTCAE v5.0)	Action Taken to Therapy	AE Management	Monitor and Follow-up
			G-CSF support may be given as deemed appropriate by the physician per institutional guidelines.	
Anemia	Grade 1	Continue dose		
	Grade 2	Continue dose		
	Grade 3	Withhold LY3475070 until resolution ≤ grade 1 then resume at one reduced DL	Blood transfusions as per local institutional guidelines	Perform CBC weekly ≤Grade 3
	Grade 4	Discontinue treatment	Blood transfusions as per local institutional guidelines	
Thrombocytopenia	Grade 1 (LLN > 75,000 mcL)	Continue dose		
	Grade 2 (75,000>25,000)	Continue dose		
	Grade 3 (<25,000 mcL) with significant bleeding	Withhold LY3475070 until resolution ≤ Grade 1 and resume treatment. If associated with bleeding, or Grade 3 reoccurs, then resume at one reduced DL. If thrombocytopenia Grade 3 reoccurs at lower DL discontinue patient.	Platelet transfusion per local institutional guidelines.	Perform CBC weekly ≤Grade 3.
	Grade 4 life threatening spontaneous bleeding	Permanently discontinue.	Platelet transfusion per local institutional guidelines	

Abbreviations: CBC = complete blood count; CCI; CCI; G-CSF  
= granulocyte colony-stimulating factor; LFTs = liver function tests; CCI.

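### The Grade 3 thrombocytopenia label in Protocol 6.6.1 requires significant bleeding, but its own action cell holds drug regardless and uses bleeding only to decide on dose reduction

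*Protocol*

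**What the plan says.** Protocol Section 6.6.1 gives its tables an operative role: "LY3475070 treatment may be interrupted, dose reduced or discontinued due to toxicity per the tables below". Rows are identified by grade or condition under CTCAE v5.0.

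The thrombocytopenia block has four rows:

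- **Grades 1 and 2** are defined by count alone (lower limit of normal to 75,000, then 75,000 to 25,000). Treatment continues.
- **Grade 3** is labelled "Grade 3 (<25,000 mcL) with significant bleeding". Its action is: "Withhold LY3475070 until resolution ≤ Grade 1 and resume treatment. If associated with bleeding, or Grade 3 reoccurs, then resume at one reduced DL". A further Grade 3 event at the lower level leads to discontinuation. The adjoining cells provide for platelet transfusion under local guidelines and a weekly blood count.
- **Grade 4** is labelled "Grade 4 life threatening spontaneous bleeding". It gives no count, and the action is permanent discontinuation.

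Two other places matter. The dose-limiting toxicity list in Section 6.1.1.1 names "Grade 3 thrombocytopenia associated with clinically significant bleeding and requiring platelet transfusion or Grade 4 thrombocytopenia of any duration", and the same section takes a patient with a DLT in the 28-day Phase 1a window off study treatment. The Schedule of Activities (Section 1.3) sets hematology weekly in Cycle 1 and every 3 weeks after that. The SAP summarises dose adjustments (Section 6.9.1) but sets no platelet rule.

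**The concern.** A row label decides who enters the row, and the action cell decides what happens to them. Here the label admits only patients with significant bleeding, while the action cell is written for a mixed group in which some bleed and some do not. A site with a patient below 25,000 and no significant bleeding has to choose which of the two to follow.

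This is a first-in-human study of a daily oral drug, and the table is where a site looks for the dosing action. If the label is followed, the table gives no instruction to hold and no shortened monitoring interval. The DLT rule does not close the gap. It applies only to the 28-day Phase 1a window, and its platelet item covers Grade 3 only with bleeding and transfusion. Phase 1b plans approximately up to 140 patients against a maximum of 62 in Phase 1a (Section 1.1), so most planned patients are never under that rule.

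**Working it through.** The plan states no figure on this point, so the check sets the row labels against the possible patients and then against the action cell.

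**1. Coverage by label.** Cross the count with bleeding status, using only the labels in 6.6.1:

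| Count | Bleeding | Row matched by label |
|---|---|---|
| Lower limit of normal to 75,000 | not life-threatening | Grade 1 |
| 75,000 to 25,000 | not life-threatening | Grade 2 |
| Below 25,000 | none, or not significant | **no row** |
| Below 25,000 | significant | Grade 3 |
| No count given | life-threatening, spontaneous | Grade 4 |

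One cell is empty. No other visible row of 6.6.1 catches it: the catch-all row is for non-hematologic toxicity, and the redacted row sits in the non-hematologic block.

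**2. Label against action cell.** Every patient who meets the label is bleeding. The condition for a reduced dose level is therefore always met, and resumption at the same dose can never apply at a first event. On recurrence the cell reduces the dose anyway. An instruction that no one can reach shows that the cell was written for a wider group than the label admits.

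**3. Comparison with the rest of the table.** Visible grade rows in 6.6.1 (redacted rows not counted): rash 4 + diarrhea 4 + liver tests 4 + fatigue 3 + other non-hematologic 4 + neutropenia 4 + anemia 4 + thrombocytopenia 4 = 31. A clinical complication appears in the label of 2 of these 31, and both are thrombocytopenia (Grades 3 and 4). Neutropenia shows the usual pattern: its Grade 3 label carries the grade only, and the complication is in the action cell: "If febrile neutropenia then dose reduce one level upon resolution ≤ grade 1".

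**4. What the empty cell loses.** By label, the patient gets neither the explicit hold nor the weekly count. After Cycle 1 the scheduled interval is 21 days instead of 7, and 21 / 7 = 3, so one scheduled count replaces three over a cycle.

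**5. Effect of correcting the Grade 3 label alone.** The limit of 25,000 has no lower bound. Once bleeding is removed as an entry condition, every count below 25,000 reaches at least the hold and the weekly count. That includes a non-bleeding Grade 4 count, which must lie below the Grade 2 floor of 25,000.

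**The case against.** The best reply is that the row explains itself. A cell that holds first and then asks about bleeding makes sense only if non-bleeding patients are held too, and a careful investigator would read it that way. Other provisions also apply whatever the label says:

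- Section 7.1 lets the investigator stop treatment for any untoward effect.
- Section 8.2.1 requires clinically significant laboratory results to be repeated until they resolve.
- Sections 6.5 and 6.5.1 provide for supportive care.
- Section 6.6.2 covers an event judged immune-related.
- Section 6.1.1.1 settles a Grade 4 count inside the Phase 1a DLT window.

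Most of this stands, and it keeps the point small. It does not remove the contradiction. The general provisions are discretionary or give no testing interval, and none tells a site whether the label or the action cell governs.

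A reader might go further and infer a second defect: that a non-bleeding Grade 4 count also matches no row label, so the Grade 4 row should be widened to require permanent discontinuation and to override the Grade 3 row. The DLT list does recognise Grade 4 thrombocytopenia without bleeding, and 5 of the 6 other visible Grade 4 rows in 6.6.1 discontinue outright (diarrhea, for example: "Permanently discontinue LY3475070 treatment"). The documents still do not support that step, for three reasons:

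- The corrected Grade 3 row already holds such a patient.
- The comparison with other rows is weaker than it looks. Of the two other hematologic Grade 4 rows, anemia discontinues, while neutropenia holds, resumes at a reduced level, and stops only under the rule "If neutropenia is longer than 5 days discontinue patient". That is 1 of 2.
- The documents give no Grade 4 platelet count. If the cut-off were taken to be 25,000, a Grade 4 row with precedence would absorb every patient in the Grade 3 row. If it were lower, only some would move. The effect of the change cannot be known from these documents.

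**Conclusion.** The Grade 3 thrombocytopenia label contradicts its own action cell and, taken literally, leaves a count below 25,000 without significant bleeding outside the table. This follows from the protocol text alone and needs no outside grading source.

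Severity is minor. The intended hold can be recovered from the action cell, and the general safeguards limit the risk. The size of the defect is one row label; its clinical frequency cannot be derived from the documents. No DLT count, RP2D, sample size or other statistical figure is affected, and the documents do not support reading the point as a flaw in the dose-finding.

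The Grade 4 row is not shown to be wrong. Whether a non-bleeding Grade 4 count outside the DLT window should lead to a hold or to permanent discontinuation is a clinical choice that the documents leave open.

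**What to change.** In the next amendment, change the Grade 3 label to *Grade 3 (<25,000 mcL), with or without bleeding*. Leave the action, transfusion and monitoring cells unchanged, so that bleeding or recurrence still decides on the reduced dose level. Any count below 25,000 then triggers at least the hold and the weekly blood count.

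Leave the Grade 4 row as written. Separately, the sponsor should check the table's cut-offs against CTCAE v5.0 and then decide whether a non-bleeding Grade 4 count outside the DLT window is held or permanently discontinued.

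The cost is one reworded label, with no new visit or patient and no test beyond the weekly count that the row already specifies. The downside is that a few non-bleeding patients may be held who might otherwise have continued.
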